**Table 4: Definitions of CTCAE Grades 1, 2, 3, and 4**

Test	Grade 1	Grade 2	Grade 3	Grade 4
ALT/SGPT	>ULN – 3 × ULN	>3–5 × ULN	>5–20 × ULN	>20 × ULN
AST/SGOT	>ULN – 3 × ULN	>3–5 × ULN	>5–20 × ULN	>20 × ULN
Alkaline phosphatase	>ULN – 2.5 × ULN	>2.5–5 × ULN	>5–20 × ULN	>20 × ULN
Total bilirubin	>ULN – 1.5 × ULN	>1.5–3 × ULN	>3–10 × ULN	>10 × ULN
Hemoglobin decreased	<LLN – 8.5 g/dL	<8.5–7.5 g/dL	<7.5–5 g/dL	<6.5 g/dL

Reference Ranges, [REDACTED]

In order to assess hepatotoxicity, all elevations in liver transaminases are evaluated using Hy's Law criteria as these help to determine the risk of drug-induced liver injury. All elevations in liver transaminases will be assessed against these criteria. Hy's Law cases have the following three components:

1. The drug causes hepatocellular injury, generally shown by a higher incidence of 3-fold or greater elevations above the ULN of ALT or AST than the (non-hepatotoxic) control drug or placebo;
2. Among trial patients showing such aminotransferase (AT) elevations, often with ATs much greater than 3×ULN, one or more patients also shows elevation of serum total bilirubin (TBL) to  $\geq 2 \times$ ULN, without initial findings of cholestasis (elevated serum ALP);
3. No other reason can be found to explain the combination of increased AT and TBL, such as viral hepatitis A, B, or C, pre-existing or acute liver disease, or another drug capable of causing the observed injury [FDA (2009)].

For patients enrolled in this study these criteria are assessed in order to determine both general liver function enzyme changes (LFEs) according to change from baseline and over course of study. In addition, the assessment of changes in ALT or AST relative to TBL allowed assessment if a signal related to DILI occurred in any individual or group of patients.

## 2.7.4 Other safety data

### 2.7.4.1 ECG and cardiac imaging data

Echocardiograms and electrocardiograms will be conducted at screening, Day 2 (ECG), Day 30 and every 3 months beginning with Month 3 through Month 18/ End of Trial (excluding Month 15).

The ECG tracings or ECG machine data will be collected for centralized review and interpretation by a cardiologist. The centralized review data will be used as the primary source for this data- although site-level echocardiogram interpretation will also be captured in the eCRF.

A 12-lead ECG will be conducted at scheduled visits of Screening, Day 2, Day 30 and every 3 months through 18 months of age and assessed by a central reviewer. The central reviewer will identify abnormal ECGs that are potentially clinically significant (PCS), based on central reviewing guidelines provided by the central cardiology vendor. Clinically significant, treatment-emergent findings of ECG, as determined by the central reviewer, will be reported as adverse events. If a site reviewer of the ECG results identifies an abnormality, it will be confirmed by the central reviewer. A listing of all PCS ECGs will be provided.

**Table 5. Criteria for Potentially Clinically Significant ECG Values**

Test / Measurement	Very Low (VL)	Very High (VH)
Heart rate (bpm)	<5 th percentile for age	>95 th percentile for age OR Change (increase) from baseline $\geq 20$ bpm
QTcB (msec)	None	$\geq 440$ msec OR Change (increase) from baseline $\geq 30$ msec
QTcF (msec)	None	$\geq 440$ msec OR Change (increase) from baseline $\geq 30$ msec

Reference: [REDACTED]

A standard transthoracic echocardiogram will be performed at screening/baseline, Day 2, Day 30, and every 3 months beginning with Month 3, through Month 12, and at the End of Trial when the patient reaches 18 months of age (or early termination). Echocardiograms will be interpreted locally and results from the local interpretation (abnormal/normal, etc.) and captured in the eCRF. Additionally, echocardiogram data will be provided to an external cardiologist for centralized review; this will be considered the primary echocardiogram source data. Clinically significant, treatment-emergent findings will be reported as AEs.

24-hour Holter monitoring will take place at screening, Days -1, 1, 2, 3, 30 and Months 2, 3, 6, 9, 12, and at the End of Trial at 18 months. Holter monitors will be provided to study sites along with a dedicated laptop for uploading the data from the memory cards for centralized review and analysis by a cardiologist within 24 hours of data upload.

#### **2.7.4.2 Vital signs**

Blood pressure, respiratory rate, pulse, body temperature, and pulse oximetry will be collected at every visit. Clinically-significant, treatment-emergent findings will be reported as adverse events.

In addition, vital signs results will be flagged as Potentially Clinically Significant (PCS) if they meet the pre-specified criteria outlined in Table 6. The number and percent of patients meeting each PCS criterion will be summarized starting at Day 1 and continuing through Month 18.

The Criteria for Potentially Clinically Significant Vital Sign Findings are presented in Table 6.

**Table 6: Criteria for Potentially Clinically Significant Vital Sign Values**

Test / Measurement	Very Low (VL)	Very High (VH)
Systolic blood pressure*	<67	>110
Diastolic blood pressure*		>64
Pulse rate**	Below 5 th percentile for age	Above 95 th percentile for age
Body Weight***	Weight <3 rd percentile for age and gender	Weight >97 th percentile for age and gender
Temperature	<35°C	>39°C

\* Adapted from NHLBI [Reference Ranges](#) for age   \*\* [Bonafide et al. Pediatrics 2013;131:e1150–e1157](#)

\*\*\* Based upon NHANES III Percentiles for age and gender

Pulse oximetry will be measured at specified time points throughout the study through a small infrared light attached to the end of the patient's finger.

#### **2.7.4.3 Physical Examination**

Physical examination will include review of the following systems: head, eyes, ears, nose, throat (HEENT), lungs/thorax, cardiovascular, abdomen, musculoskeletal, neurologic, dermatologic, lymphatic, head circumference and genitourinary.

Treatment-emergent abnormal findings on physical examination will be tracked as adverse events. Any post-infusion abnormal physical exam findings will be listed by patient with the corresponding result on the baseline physical examination.

#### **2.7.4.4 Use of Non-Oral Feeding Support**

A swallowing test will be performed at baseline and every 6 months through Month 18/End of study to determine if the patient has signs of aspiration. If the test is positive for aspiration, the patient will be recommended to use an alternative method to oral feeding. Once implemented, a non-oral method of feeding support may later be removed. For each placement or removal event, the type of support (type of tube), date of placement, and date of removal will be noted. Actual use of non-oral feeding support will be quantified through the recording of volume, frequency of use, duration, and calories.

#### **2.7.4.5 Immunology**

Immunoreactivity to AAV9 and SMN will be measured in antibody titer levels (in 2-fold serial dilutions) as determined by enzyme-linked immunosorbent assays (ELISAs).

---

Immunoreactivity to AAV9 and hSMN will be monitored by the collection of samples at Screening, Day 7, Day 14, Day 21, and Day 30. Antibody titers  $>1:50$  are considered positive for antibody response while antibody titers  $\leq 1:50$  are considered negative.

Immunology variables include: mother's serum binding antibody titer to AAV9, serum binding antibody titer to AAV9, binding antibody titer to SMN.

## **2.8 Pharmacokinetic endpoints**

None.

## **2.9 PD and PK/PD analyses**

Not applicable.

## **2.10 Patient-reported outcomes**

None.

[figure not shown]
## **2.11 Biomarkers**

Not applicable.

## **2.12 Other Exploratory analyses**

All protocol deviations will be recorded in the clinical database and will be categorized in accord with Novartis Gene Therapies SOPs. Protocol deviations will be described by individual data listings.

Supportive (exploratory) efficacy variables are as follows:

**Table 7: Third Percentile Weights for Age and Gender**

Age	Gender	Weight (kg)
14 months	Male	8.2
	Female	7.5
18 months	Male	8.9
	Female	8.2

Reference: [http://www.who.int/childgrowth/standards/Technical\\_report.pdf](http://www.who.int/childgrowth/standards/Technical_report.pdf) (Table 39 and Table 50).

- Achievement of Developmental Milestones is based on video confirmed central reviewed at any visit during the study.

Exploratory endpoint data will be presented in data listings and patient profiles for the ITT population and, where appropriate, for the Ability to Thrive ITT population.

## 2.13 Interim analysis

Not applicable.

## 3 Sample size calculation

The study was originally designed to have sufficient power, when combined with an identically designed study COAV101A12301 (AVXS-101-CL-302), to establish efficacy with regard to the primary and secondary endpoints. Due to the change in data analysis and narrowed scope of COAV101A12304 (OAV101-CL-306), no combined analysis or stand-alone analysis will be conducted.

## 4 Change to protocol specified analyses

Due to the narrowed scope of COAV101A12304 (AVXS 101 CL 306) and limited subjects enrolled, only individual data listings and patient profiles will be generated, with the exception of three AE summary tables. There are no changes to analyses planned in protocol version 6.0.

## 5 Appendix

### 5.1 Imputation rules

Missing values in any of the endpoints will not be imputed when reporting these endpoints by means of individual data listings. For the CHOP-INTEND and BAYLEY instruments, rules

---

suggested by the producers of these assessments will be followed in calculating scores when individual question/items may be missing. If these rules are not enough for calculating a score, then the endpoint will be considered as having a missing value.

Missing values for safety endpoints will not be imputed.

### **5.1.1 Study drug**

If the date of study drug application will be missing or partial, it will be imputed by the date of the Day 1 visit.

### **5.1.2 AE date imputation**

Missing or incomplete AE start dates will be imputed according to the general Novartis imputation rules:

- If the day is missing then use '01'
- If the day and month is missing use '01JUL'
- If the imputation of a start date causes the start date to be after the non-missing end date, then the start date is set to the same date as the end date.
- If the imputation of a start date causes the start date to be prior to the start of treatment (when the event should be on-treatment), then the start date is set to the same date as the treatment date +1.
- If the imputation of a start date causes the start date to be after the start of treatment (when the event should be before start of treatment), then the start date is set to the treatment date.

AE end dates will not be imputed.

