13. ADVERSE AND SERIOUS ADVERSE EVENTS

13.1. Definition of Adverse Events

13.1.1. Adverse Event

An AE is the development of an undesirable medical condition or the deterioration of a pre-existing medical condition following or during exposure to a pharmaceutical product, whether or not considered causally related to the product. In clinical studies, an AE can include an undesirable medical condition occurring at any time, including baseline or washout periods, even if no trial treatment has been administered.

All AEs (related or not related) that occur after signing of the informed consent through the last trial visit will be collected and recorded in the eCRF.

All AEs will be classified in accordance with the CTCAE version 4.03 (or later version, upon agreement of Novartis Gene Therapies) outlined in Table 4.

Table 4 - Common Terminology Criteria for Adverse Events

Grade	Definition
1	Mild; asymptomatic or mild symptoms; clinical or diagnostic observations only; intervention not indicated
2	Moderate; minimal, local or noninvasive intervention indicated; limiting age-appropriate instrumental ADL. ^a
3	Severe or medically significant, but not immediately life-threatening; hospitalization or prolongation of hospitalization indicated; disabling; limiting self-care ADL. ^b
4	Life-threatening consequences; urgent intervention indicated.
5	Death related to AE.

Source: Common Terminology Criteria for Adverse Events (version 4.03) [[NCI, 2010](#)]

^a ADL, Activities of daily living; Instrumental ADL refer to preparing meals, shopping for groceries or clothes, using the telephone, managing money, etc.

^b Self-care ADL refer to bathing, dressing and undressing, feeding self, using the toilet, taking medications, and not bedridden.

Additionally, a DSMB/DMC will review safety data on a quarterly basis. A detailed description of the DSMB/DMC, its role in this trial, and the timing and process of the scheduled reviews will be described in a DSMB/DMC Charter.

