### 2.1.1 General definitions

“Day 1” is defined as the day of gene transfer, “Day -1” the day before. Gene transfer is the single-time study treatment as gene therapy infusion. The dose is the total vector genome (vg) delivered, the human SMN cDNA sequence, corresponding to the mature mRNA, cloned into the self-complementary AAV vector plasmid, given in vg per subject weight in kilogram (kg) on Day -1.

For any event, “study day” is defined as the time from Day 1 to the day of the event in days plus 1 day.

“Baseline” refers to a non-missing measurement or evaluation made prior to initiation of gene therapy infusion. If there are multiple measurements prior to the initiation of gene therapy infusion, only the latest measurement will be considered as baseline for analysis purposes. If these multiple measurements occur at the same time or time is not available, then the average of these measurements (for continuous data) or the worst among these measurements (for categorical data) will be considered as the baseline value. This same baseline value will be used for the treatment and post-treatment periods.

“Last contact” refers to the last study visit. If not terminated early, it is the end-of-trial visit at 18 months of age. “Age” will be expressed in months and rounded to one decimal place, where age in months is the time from birth to a date in days, plus 1 day, divided by 30. The final value for each patient is the first non-missing value on or after the participant reaches 18 months of age (540 days) with an upper limit of 570 days. Thus, the earliest visit between 540 and 570 days of age, inclusive, will be used in the “18 months of age” analysis.

Analysis visits are defined per month following a visit windowing approach in two different schedules, one based on study day post dosing and another one based on patient age. For by-visit efficacy endpoints, the time windows describe how efficacy data will be assigned to protocol-specified time points. For a Month K,  $K > 1$ , the time windows are around Study Day  $K*30$ , the nominal time, in a range of -15 to +14 days. Month 1 spans from Study Day 1 to 44. If more than one efficacy observation for a specific assessment is included in a time window, the assessment closer to the nominal time will be used. If there are two efficacy observations

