equally distant to the nominal time, the latest one will be used in analyses. Visits at 14 and 18 Months of Age follow an analysis window of 420 to 434 and 540 to 554 days of age, respectively. CHOP-INTEND scores and Bayley Scales will also be presented by analysis visit following an age based visit windowing approach for M months of age in the range of  $M*30$  to  $(M+1)*30-1$  days since birth.

“Bilevel Positive Airway Pressure” (BiPAP) is a form of non-invasive mechanical pressure support ventilation.

---

“Permanent ventilation” is defined as a requirement of  $\geq 16$ -hour respiratory assistance per day (includes BiPAP) continuously for  $\geq 14$  days in the absence of an acute reversible illness, excluding perioperative ventilation.

A “responder” is a patient who demonstrates achievement of an endpoint at any post-procedure visit up to and including the 18-months-of-age visit.

An “Adverse Event” (AE) is any untoward medical occurrence in a clinical investigation subject, which does not necessarily have a causal relationship with the drug or device under study.

A “treatment-emergent Adverse Event” (TEAE) is any AE whose onset or worsening occurred on or post Day 1.

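### SAP 5.1.2 gives no default for an AE whose partial start date spans the infusion, and its rule for known pre-treatment events can place them on Day 1

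*SAP*

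**What the plan says.** SAP 5.1.2 (AE date imputation) has five rules for AE start dates:

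1. "If the day is missing then use '01", that is, the first of the month.
2. "If the day and month is missing use '01JUL", that is, 1 July.
3. A start imputed later than a known end date is set to the end date.
4. A start imputed before treatment is moved forward, but conditionally: "when the event should be on-treatment), then the start date is set to the same date as the treatment date +1".
5. A start imputed after treatment is moved back, again conditionally: "when the event should be before start of treatment), then the start date is set to the treatment date".

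Under SAP 2.1.1, a treatment-emergent AE "is any AE whose onset or worsening occurred on or post Day 1", and Day 1 "is defined as the day of gene transfer".

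Protocol 13.1.1 sets the collection window: "All AEs (related or not related) that occur after signing of the informed consent through the last trial visit will be collected". Consent is obtained in screening, Days -30 to -2 (SAP 1.1).

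SAP 4 limits the output to listings and patient profiles plus three AE summary tables. SAP 2.7 and 2.7.1 identify these as TEAEs, serious TEAEs and an overview.

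**The concern.** Whether an AE is treatment-emergent depends on its start date relative to Day 1. When the recorded part of the date covers days on both sides of the infusion, the imputation rule decides the classification. Rules 1 and 2 pick a fixed calendar date without regard to the infusion. Rules 4 and 5 correct the result only if someone has already decided on which side of treatment the event belongs. The SAP does not say who decides, on what evidence, or what happens if it cannot be decided. A missing date is the situation in which that is most likely to be unknown.

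At stake is whether an event appears in two of the three planned AE tables and in the overview's TEAE rows (related, Grade 3 and 4, serious, special interest and others). With 2 patients, if the event is a patient's only one in a row, misclassifying it moves the row from 1/2 (50%) to 0/2 (0%), or the reverse.

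**Working it through.** The plan states no figure on this point, so there is none to reproduce. The check applies the five rules literally.

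**Assumptions.** An illustrative 365-day year; every infusion date and every onset day weighted equally; true onset on or after Day 1; no AE end date; no later worsening that would itself make the AE treatment-emergent. An event is lost if its imputed start is before Day 1.

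**Day missing, AE in the infusion month.** A month of *m* days has *m*(*m*+1)/2 combinations of infusion date and onset day on or after infusion.
- Total: 7 × 496 (31-day months) + 4 × 465 (30-day months) + 406 (February) = 5,738.
- With timing undetermined, rule 4 is not triggered and the start stays on the 1st. That precedes Day 1 unless infusion was itself on the 1st. Infusions on the 1st account for 365 combinations (the month lengths added up).
- Lost: 5,738 − 365 = 5,373, or 5,373/5,738 = 93.6%.
- If the event is recognised as on-treatment, rule 4 moves it to Day 2 and 0 of 5,738 are lost.

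**Day and month missing, AE in the infusion year.**
- Total: 365 × 366/2 = 66,795.
- With timing undetermined, the start is 1 July. That precedes Day 1 for infusions from 2 July to 31 December, which is 183 dates.
- Lost: 183 × 184/2 = 16,836, or 16,836/66,795 = 25.2%.
- If recognised as on-treatment, 0 of 66,795 are lost.

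**Opposite direction (rule 5).** Take a known pre-treatment event with only the year recorded. For an infusion before 1 July (31+28+31+30+31+30 = 181 dates), 1 July is after treatment, so rule 5 sets the start to the treatment date. That is Day 1, and the event qualifies as a TEAE because its onset is now "whose onset or worsening occurred on or post Day 1". For an infusion on 1 July the imputed date is already Day 1, making 182 of 365 dates. On 1 January this is only formal, since no earlier onset is possible in that year. A known end date before infusion prevents the error through rule 3. When the month is known, the 1st is never later than the infusion for a pre-treatment event, so rule 5 has nothing to correct.

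**Example: infusion 15 March, AE recorded as March with no day.**

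| Handling | Imputed start | TEAE? |
|---|---|---|
| Recognised as on-treatment (rule 4) | 16 March | Yes |
| Undetermined | 1 March | No |
| Undetermined, not before consent, consent at Day -30 | 1 March | No |
| Undetermined, not before consent, consent at Day -2 | 13 March | No |
| Undetermined, default to infusion date | 15 March | Yes |

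In the same enumeration, a consent-date floor leaves both losses unchanged (93.6% and 25.2%). Defaulting to the infusion date brings both to 0%.

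**The case against.** The strongest reply is that the SAP already has a safeguard. Rule 4 rescues every event recognised as on-treatment, and the SAP never says that an undetermined event is to be treated as pre-treatment. The rules are described as general company rules, and a standard outside these documents may supply the criterion. This stands in part. The loss is confined to events of undetermined timing, and the classification follows from a literal reading, not from an explicit instruction. A programmer working from the SAP alone still has no criterion and no default.

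Partial dates should also be rare. Onset date is recorded, with time during the inpatient period (Protocol 13.3). Visits are frequent, SAEs are recorded within 24 hours of the site becoming aware, and 2 patients are shown individually. This stands and limits the practical effect.

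A reader might go further and infer that:
- **The missing consent-date floor causes the loss.** It cannot. Consent always precedes Day 1, so a floor only exchanges one pre-treatment date for another. The floor is a plausibility matter: for an infusion on 1 August, Day -30 is 2 July, so an imputed 1 July falls before the screening window. Even that is not absolute, because antibody retesting (exclusion criterion 11) may lengthen the interval from consent to dosing.
- **Affected events vanish from the report.** They do not. They stay in the listings and in the overview's any-AE and any-serious-AE rows (SAP 2.7.1).
- **The section consistently hides treatment-emergent events.** It does not. Rule 5 errs the other way.

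**Conclusion.** The gap is real and narrow. SAP 5.1.2 does not say how on-treatment status is decided or what to do when it is undetermined. An AE whose partial date spans the infusion can therefore be left before Day 1 and out of the TEAE counts. Rule 5 can also bring known pre-treatment events into those counts.

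The 93.6% and 25.2% describe how the rule behaves under equal weighting, with timing undetermined and no end date. They are not forecasts of lost events, since the documents give no rate of partial dates. With 2 patients, individual listings and no inference, the expected effect is small. The case for changing the text is that the TEAE tables are among the few aggregate outputs and the correction costs almost nothing.

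**What to change.** Replace the conditional corrections in SAP 5.1.2 with wording such as:

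> *If the known part of the AE start date spans the infusion date (same month with day missing, same year with day and month missing, or date fully missing), and neither the AE end date nor other documentation shows onset before infusion, impute the infusion date and count the AE as treatment-emergent. Partial dates wholly after the infusion month or year keep their known month or year. Known pre-treatment events are imputed to a date no later than the day before infusion.*

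The limit to spanning dates is needed. Without it, an AE known to have started in June after a March infusion could be re-dated to March.

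Two related edits belong in the same change:
- As a plausibility check only, no imputed AE date may precede informed consent. This is compatible with the limit for pre-treatment events, because consent is given by Day -2.
- SAP 5.1 says that missing values for safety endpoints are not imputed. State that AE start dates are an exception, so that it agrees with 5.1.2.

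The cost is SAP wording and a small programming change. The downside is that a few pre-dose events may be counted as treatment-emergent.

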## **2 Statistical methods**

### **2.1 Data analysis general information**

Novartis Gene Therapies, Inc. will be performing final analysis.

Analyses will be performed using [REDACTED]

There are no interim analyses. The final analysis will be composed by individual data listings and patient profiles after the final database lock. No data aggregations, summary tables or inferential statistical approaches will be performed.

---

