### **2.7 Safety analyses**

Safety will be assessed through the incidence and severity of AEs, vital sign assessments, cardiac assessments, laboratory evaluations (chemistry, hematology, immunology, urinalysis), physical examinations, and use of concomitant medications. Adverse events will be coded in accordance with the most current version of the MedDRA coding dictionary. Safety assessments will be presented in data listings or patient profiles for the safety population. In addition, summary tables will be prepared for treatment-emergent AEs and SAEs together with an overview of AEs.

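### SAP 5.1.2 can move an adverse event known to precede treatment onto Day 1, where SAP 2.1.1 counts it as treatment-emergent

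*SAP*

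**What the plan says.** SAP 5.1.2 gives the rules for incomplete adverse event start dates. A missing day becomes the first of the month, and a missing day and month become 1 July. Three adjustments follow:

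- If the imputed start is later than a known end date, "then the start date is set to the same date as the end date".
- If the event belongs to the on-treatment period but the imputed start is before treatment, "then the start date is set to the same date as the treatment date +1".
- If the imputed start is after treatment "when the event should be before start of treatment), then the start date is set to the treatment date".

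End dates are never imputed.

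In SAP 2.1.1, Day 1 "is defined as the day of gene transfer", and a treatment-emergent event is "any AE whose onset or worsening occurred on or post Day 1".

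SAP 2.1 states "No data aggregations, summary tables or inferential statistical approaches will be performed", but SAP 2.7 is more specific: "summary tables will be prepared for treatment-emergent AEs and SAEs together with an overview of AEs". SAP 4 confirms that three adverse event tables are kept. Protocol 13.1.1 collects adverse events from signing of consent, so pre-treatment events are in the database.

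**The concern.** The last adjustment in SAP 5.1.2 deals with an event whose pre-treatment status is already known, yet it assigns the one date that SAP 2.1.1 places inside the treatment-emergent window. The two sections put the treatment date on opposite sides of the boundary. In 5.1.2, on-treatment events go to the day after treatment and pre-treatment events to the treatment date itself. In 2.1.1, the treatment date is already treatment-emergent. No sentence carries the known pre-treatment status into the flag.

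The flag drives the tables of treatment-emergent and serious treatment-emergent events and several rows of the overview. These three tables are the adverse event summaries that SAP 4 exempts from the listings-only approach.

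**Working it through.** The plan gives no figure on this point, so the check applies the written rules to all possible treatment dates.

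**Inputs**
- Year-only onset is imputed to 1 July of that year; end-date cap; reset to the treatment date (SAP 5.1.2).
- Treatment-emergent if the start date is on or after the treatment date (SAP 2.1.1). The SAP gives no other derivation of the flag.
- Illustrative grid: 365 treatment dates (2019) × true onset 1 to 30 days earlier = 10,950 combinations per end-date case. The event is known to precede treatment and does not worsen after dosing.

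**One record traced through**
- Treatment 20 May 2019, onset year 2019, no end date. Imputed start 1 July 2019; this is after treatment, so it is reset to 20 May 2019 = Day 1. Treatment-emergent: yes.
- Same record, treatment 20 August 2019. Imputed start 1 July 2019 precedes treatment and stands. Treatment-emergent: no.

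**Which treatment dates are affected**
- 2 January to 30 June: 1 July falls after treatment. With the end date missing or after treatment, the reset gives the treatment date. With the end date on the treatment date, the end-date cap gives the same result.
- 1 July: the imputed date is itself Day 1, so no adjustment is needed to produce the error.
- After 1 July: the imputed date precedes treatment; no error.
- Onset in the preceding calendar year: 1 July of that year precedes treatment; no error.

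Affected dates: 30 (January) + 28 + 31 + 30 + 31 + 30 (February to June) + 1 = 181 of 365; 182 of 366 in a leap year.

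**Count on the grid**
- Treatment 2 to 31 January: 1 + 2 + … + 30 = 465 combinations with onset in the same year.
- Treatment 1 February to 1 July: 151 dates × 30 = 4,530.
- Total: 465 + 4,530 = 4,995 of 10,950, of which 30 have treatment on 1 July and 4,965 come from the reset or the cap.

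Combinations wrongly flagged, by end date and rule:

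| End date | SAP rule | Day before treatment, trigger still after treatment (cap applied first) | Day before treatment, trigger on or after treatment |
|---|---|---|---|
| Missing | 4,995 | 30 | 0 |
| 10 days after treatment | 4,995 | 30 | 0 |
| On the treatment date | 4,995 | 4,995 | 0 |
| Before treatment | 0 | 0 | 0 |

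Under the SAP rule and under the last column, the totals do not depend on the order in which the adjustments are applied. A leap year gives 5,025 of 10,980 in each of the three affected cases. With only the day missing, the count is 0 throughout.

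These counts show when the rule fails, not how often it will. They are conditional on a year-only onset and assume treatment dates spread evenly over the year, whereas the trial has 2 patients.

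**The case against.** The strongest objection is that SAP 2.1.1 defines a treatment-emergent event by when onset occurred, not by an imputed date. The reset fires only when the event is already known to precede treatment, so a programmer could keep that status and ignore the placeholder. It is true that the SAP never states that the flag is computed from the imputed date. But it gives no other derivation, and adjustments that depend on whether an event is pre-treatment or on-treatment would do little if the flag ignored them. Stating that the known status governs is one way to repair the text.

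Two other passages might seem to remove the problem. SAP 5.1 says that missing safety endpoints are not imputed, but 5.1.2 imputes start dates explicitly and is the more specific rule. The protocol's abbreviation list defines Day 1 as a 24-hour interval from the start of infusion, but the SAP's study day "is defined as the time from Day 1 to the day of the event in days plus 1 day", and an imputed date carries no time.

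The objection on rarity stands. Protocol 13.3 requires an onset date for every event, with time in the inpatient period. Screening starts no earlier than Day -30, so a pre-treatment event recorded only by year would be unusual. Over-counting is also the more cautious direction for safety, and the listings still show the data.

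The same reset appears in SAP 5.1.3.1 for prior therapies. It does not feed the treatment-emergent flag, but the two sections would differ if only 5.1.2 were changed.

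**Conclusion.** The concern holds, as a minor point. As written, the rule misclassifies a known pre-treatment event when the onset is known only by year, treatment falls from 2 January to 1 July of that year, no end date precedes treatment, and the event did not worsen on or after Day 1. The conclusion rests on the flag being derived from the imputed date.

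The date arithmetic is certain; an actual effect is not shown. Enrollment closed with 2 patients and no such record is documented. If one existed, a preferred term would change from 0/2 to 1/2 patients in the treatment-emergent table, and likewise in the serious table if the event was serious.

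**What to change.** In SAP 5.1.2, after the end-date cap, replace the last adjustment with this: if the event is known to precede treatment and the imputed start is on or after the treatment date, set the start to the day before treatment. The trigger must include the treatment date itself. Otherwise treatment on 1 July, and events ending on the treatment date, stay misclassified.

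Alternatively, leave 5.1.2 as it is and add a sentence to SAP 2.1.1: an event known to have started before treatment is not treatment-emergent unless it worsened on or after Day 1.

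Either change costs one bullet or sentence and the matching code. The first departs from the sponsor's general imputation rules; the second does not.
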